6.6.5 Exploratory Efficacy Analysis

The exploratory efficacy endpoints are identified in Section [2.1.3](#).

The exploratory endpoints will be summarized using tables, listings, and graphs, as appropriate. Additional statistical modeling may be considered (e.g., ANCOVA, logistic regression).

6.6.6 Historical Controls

Should the treatment discontinuation rate in the placebo arm be significantly higher than expected, the Sponsor may consider the use of historical controls for efficacy analysis. In this scenario, the use of historical controls will be deemed supportive analyses.

Prior to database lock, the Sponsor may select historical controls from ENROLL-HD. These historical controls may be selected to match patients with regard to important baseline characteristics (e.g., gender, CAG, age, IS, International Standard Classification of Education). The objective for use and exact algorithm for selecting historical controls will be specified in the SAP. If implemented, the actual selection will

be made before database lock and unblinding of treatment allocation and will be documented and stored in the Sponsor's database.

Whether the Sponsor will decide to use those the historical controls, the exact algorithm for borrowing and for deriving an overall treatment effect will be described in the SAP before unblinding.

Additionally, given that some of the patients who will be enrolled in this study may have been part of ENROLL-HD, the Sponsor may explore a within-patient comparison for the rate of decline in cUHDRS or TFC score, before treatment with RO7234292 (prior to randomization, using ENROLL-HD registry data) and after treatment with RO7234292 (after randomization, using study data), for patients who were randomized to the active arm and had follow-up in ENROLL-HD of at least 1 year's duration prior to randomization into this study.

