3. STUDY DESIGN

3.1 DESCRIPTION OF THE STUDY

3.1.1 Overview of Study Design

Study BN40423 is a Phase III, randomized, placebo-controlled, double-blind, multicenter clinical study to evaluate the efficacy, safety, PK, and biomarker effects of intrathecally administered RO7234292 in patients with manifest HD.

Effective 22 March 2021, no further study treatment will be administered in this study. Patients on the study will continue to be followed for safety and efficacy outcomes until study completion (see Section 3.1.1.1, [Appendix 1a](#), and [Appendix 1b](#)).

Prospective patients will undergo screening assessments during a 4-week screening period. A maximum of one re-screening will be allowed within 8 weeks of the initial screening failure for patients who fail the initial screening (see Section 4.5.1). If re-screening is required, the CAG repeat length testing from the initial screening does not need to be repeated (historical values prior to screening will not be accepted). The screening MRI and viral serology from the initial screening, including from other Roche RO7234292 studies, may be acceptable as part of the re-screening assessments if performed within 12 weeks of the baseline visit.

Upon completion of the screening period, eligible patients will be randomly allocated in a 1:1:1 ratio to receive RO7234292 Q8W (RO7234292 Q8W arm), RO7234292 Q16W (RO7234292 Q16W arm), or placebo Q8W (placebo arm) by IT injection, as described in [Table 1](#). To maintain the study blind and integrity, patients in the RO7234292 Q16W arm will also receive placebo (i.e., alternating doses of active drug and placebo).

Table 1 Treatment Regimens after Implementation of Protocol Version 4

Arm	Treatment Regimen
RO7234292 Q8W arm	RO7234292 loading dose: 120 mg at Days 1 and 29 (2 doses) RO7234292: 120 mg Q8W from Week 13 to Week 93 (11 doses)
RO7234292 Q16W arm	RO7234292 loading dose: 120 mg at Days 1 and 29 (2 doses) RO7234292: 120 mg Q16W from Week 21 to Week 85 (5 doses) Placebo: Q16W from Week 13 to Week 93 (6 doses)
Placebo arm	Placebo: at Days 1 and 29 (2 doses) and Q8W from Week 13 to Week 93 (11 doses)

Q8W =every 8 weeks; Q16W =every 16 weeks.

Note: Effective 22 March 2021, no further study treatment will be administered in this study.

During scheduled clinic visits, patients will undergo safety and tolerability evaluations that include neurologic examinations, vital signs, ECGs, clinical laboratory tests, MoCA,

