6.2 DETERMINATION OF SAMPLE SIZE

The planned sample size is adequate to capture meaningful clinical decline on both the TFC and cUHDRS and was estimated on the basis of data available from non-interventional studies (TRACK-HD, COHORT, ENROLL-HD) and a randomized placebo-controlled study (2CARE). Based on these data, using the anticipated trial population, a meta-analysis for the change from baseline at 24 months in TFC score suggested a natural decline of 1.36 points and a corresponding pooled standard deviation of 1.78. A conservative treatment discontinuation rate at Week 101 for patients receiving placebo or active is assumed to be 20% and 15%, respectively. Using these assumptions, the simulation described below was performed to estimate the sample size.

Description of Simulations to Derive the Sample Size

The design used for the simulation was simplified to consider only 2 treatment arms (placebo and active) and 2 postbaseline timepoints (Week 49 and Week 101). These simplifications are justifiable given that:

- The overall alpha level 5% will be split to 2.5%, such that each active treatment will be tested against placebo independently. Within each testing chain, a hierarchical procedure will be used to test the primary endpoint and secondary endpoints (see Section 6.3).
- The difference on the derived sample size for considering more than two postbaseline timepoints would be minimal.

The following algorithm was run and repeated 500,000 times:

1. Generate change from baseline values in TFC at Week 49 and Week 101 for N active patients according to the following bivariate normal distribution:

$$\begin{pmatrix} y_{wk49} \\ y_{wk101} \end{pmatrix} = N \left(\mu = \begin{pmatrix} 0.47 \\ 0.82 \end{pmatrix}, \sum = \begin{pmatrix} 1.56^2 & 1.8 \\ 1.8 & 1.78^2 \end{pmatrix} \right)$$

where y_{wk49} and y_{wk101} is the change from baseline in TFC, respectively, at Week 49 and Week 101, μ is the assumed true change at those two timepoints, and Σ is the variance-covariance matrix. Subsequently:

- set to missing, due to study drug-related (SDR) reasons, both values at Week 49 and Week 101 for 5% of the N patients. Set to missing, due to non-study drug-related (NSDR) reasons, both values at Week 49 and Week 101 for additional 2.5% of the N active patients.

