- set to missing, due to SDR reasons, only the value at Week 101 for additional 5% of the N active patients. Set to missing, due to NSDR reasons, only the value at Week 101 for additional 2.5% of the N active patients.

2. Generate change from baseline values in TFC at Week 49 and Week 101 for N placebo patients according to the following bivariate normal distribution:

$$\begin{pmatrix} y_{wk49} \\ y_{wk101} \end{pmatrix} = N \left(\mu = \begin{pmatrix} 0.79 \\ 1.36 \end{pmatrix}, \Sigma = \begin{pmatrix} 1.56^2 & 1.8 \\ 1.8 & 1.78^2 \end{pmatrix} \right)$$

where y_{wk49} and y_{wk101} is the change from baseline in TFC, respectively, at Week 49 and Week 101, μ is the assumed true change at those two timepoints, and Σ is the variance-covariance matrix. Subsequently:

- set to missing both values at Week 49 and Week 101 for 10% of the N placebo patients
- set to missing only the value at Week 101 for additional 10% of the N placebo patients

Given how missing data will be imputed, it is not relevant to differentiate missing data into SDR versus NSDR reasons for placebo patients.

3. Apply multiple imputations and derive 20 complete datasets. Missing data on placebo patients were imputed from the placebo arm. Missing data on active patients, depending on if due to NSDR or SDR reasons, were imputed respectively from the active or the placebo arm.

4. Use a t-test to compare active versus placebo at Week 101 for each completed dataset and pool the result (Rubin 1987) to derive an estimate of the treatment effect, including a p-value.

Across the 500,000 simulations, the power achieved, with the N patients per arm was calculated by dividing the number of times the p-value (in above Step 4) was below 2.5%

by 500,000. The above procedure was repeated by only changing the N until the calculated power was close to 80%.

It was estimated that 267 patients per arm will provide approximately 80% power, at a two-sided $\alpha = 0.025$ level, to detect a 40% slowing of clinical decline for RO7234292 as compared with placebo at 101 weeks. This treatment effect translates into an expected average decline of ~0.82 points at 101 weeks for the RO7234292 arms. The minimal detectable difference with these assumptions is ~0.38 points.

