6.6.2 Primary Efficacy Analysis

The primary efficacy endpoint is the change from baseline in cUHDRS score at Week 101. This is defined as the attribute "variable" of the primary estimand in Section 6.6.1.

Note: The primary efficacy endpoint for the U.S. FDA will be change from baseline in the TFC score at Week 101. TFC will be analyzed the same way as the cUHDRS.

The primary efficacy analysis for this study will compare each active treatment arm, RO7234292 Q8W and RO7234292 Q16W, against the placebo arm.

To account for the multiple comparison, an appropriate procedure will be used to maintain the overall two-sided type I error at 5% (details will be given in the SAP).

The analysis of the primary endpoint will be performed by means of analysis of covariance (ANCOVA). The model will include the corresponding endpoint baseline score, CAG repeat length, baseline CAP score (defined in Section 4.1.1), and treatment as covariates. On the basis of this analysis, least squares mean for the treatment differences at Week 101 and corresponding 95% CIs will be derived.

The robustness of the primary method of estimation described above may be explored by alternative sensitivity estimators based on varying assumptions underlying the multiple imputation strategy. These sensitivity analyses will be described in the SAP.

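### The exploratory before/after comparison with ENROLL-HD is limited to active-arm patients, so a change in rate unrelated to drug cannot be separated from a drug effect; placebo patients should be included

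*Protocol*

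**What the plan says.** The last paragraph of Protocol section 6.6.6 notes that "some of the patients who will be enrolled in this study may have been part of ENROLL-HD" and that, for this reason, "the Sponsor may explore a within-patient comparison for the rate of decline in cUHDRS or TFC score". The before period is ENROLL-HD registry data up to randomization. The after period is defined as "after treatment with RO7234292 (after randomization, using study data"). The population is fixed as active patients only: "for patients who were randomized to the active arm and had follow-up in ENROLL-HD of at least 1 year's duration prior to randomization".

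The paragraph names no placebo counterpart, no adjustment for a change of rate over time and no cut-off for the after period. Section 6.6.6 does defer details to the SAP, but those deferrals concern how historical controls are selected and borrowed from. This paragraph defers nothing.

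Two other places bear on the point. Section 3.1.1 states that "eligible patients will be randomly allocated in a 1:1:1 ratio" to Q8W, Q16W or placebo. Section 6.6.2 places the efficacy inference elsewhere: "The primary efficacy analysis for this study will compare each active treatment arm, RO7234292 Q8W and RO7234292 Q16W, against the placebo arm".

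**The concern.** A one-group before/after contrast carries everything that changes at randomization, not only the drug. At least three other things may change here.

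- **Natural course.** The untreated rate of decline need not be constant over the years being compared.
- **Measurement.** The trial prescribes companion input to the TFC and a fixed order of assessments (sections 4.5.9 and 4.5.9.2, Appendix 5). The protocol does not say that the registry ratings were made in the same way.
- **Selection at entry.** Section 4.1.1 requires a stable medical, psychiatric and neurological condition for 12 weeks before screening.

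If such shifts make the trial slope shallower than the registry slope, an inert drug appears to slow decline. If they make it steeper, a real benefit is hidden or harm is overstated. Section 6.6 excludes patients enrolled before Version 4 from the efficacy analyses so that the groups compared are concurrent. The paragraph in 6.6.6 sets the concurrent control aside.

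Version 6 adds a second difficulty. Dosing ended on 22 March 2021 and patients are followed off drug to Week 101, so the after period as worded mixes time on and off drug.

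**Working it through.** **1. What the contrast estimates.** Let *s* be the average change in slope from registry to trial that would occur without drug, and *d* the effect of drug on slope.

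- Active patients, after minus before: *s + d*
- Placebo patients, after minus before: *s*
- Difference between arms: (*s + d*) − *s* = *d*

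The active-only version returns *s + d* and cannot separate the two. Having ENROLL-HD history is fixed before randomization, so the comparison between arms within that subset is still randomized and *s* has the same expectation in each arm.

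**2. Are such placebo patients likely to exist?** Section 6.6.6 does not tie registry history to an arm. Under 1:1:1 allocation, about one third of patients with that history are expected on placebo, with TFC and cUHDRS on the same visit schedule (Appendix 1a). No count is given, so this is an inference.

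**3. Can the protocol's planning figures be relied on?** The before/after comparison has no stated figure of its own. The section 6.2 inputs were checked because step 4 uses them.

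- Planned slowing: 1 − 0.82/1.36 = 39.7%, stated as 40%.
- Re-running the section 6.2 algorithm at 267 per arm (20 imputations, 4,000 replicates instead of 500,000) gives power 0.800, stated as approximately 80%.
- Minimal detectable difference: z(0.9875) × 1.78 × √[1/(0.80 × 267) + 1/(0.85 × 267)] = 0.380, stated as about 0.38.

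The plan's figures reproduce.

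**4. Does the protocol assume a constant untreated rate?** Placebo planning means are 0.79 at Week 49 and 1.36 at Week 101.

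- To Week 49: 0.79/48 = 0.0165 points per week.
- Week 49 to Week 101: (1.36 − 0.79)/52 = 0.0110 points per week.
- Change: 1 − 0.01096/0.01646 = 33% lower (32% if the first interval is counted as 49 weeks).

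So it does not. Both intervals lie after randomization, however, so this is not the registry-to-trial shift *s*.

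**5. Can *s* be computed?** No pre-randomization rate is given. The whole-study placebo rate is 1.36/100 = 0.0136 points per week. Taking the two rates from step 4 as hypothetical registry rates:

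- registry rate 0.01646: 1 − 0.0136/0.01646 = 17% apparent slowing;
- registry rate 0.01096: 0.0136/0.01096 − 1 = 24% apparent acceleration.

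The sign itself depends on the unknown rate.

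**6. Illustration under a stated assumption.** Section 6.2 reports that the source data "suggested a natural decline of 1.36 points and a corresponding pooled standard deviation of 1.78" over 24 months. Assume a registry rate of 1.36/2 = 0.68 points per year and no drug effect. The planned difference is 1.36 − 0.82 = 0.54.

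| Assumed natural slowing | Apparent gain over 2 years | Share of 0.54 |
|---|---|---|
| 10% | 0.68 × 0.10 × 2 = 0.14 | 25% |
| 20% | 0.68 × 0.20 × 2 = 0.27 | 50% |
| 30% | 0.68 × 0.30 × 2 = 0.41 | 76% |

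An equal acceleration gives the same figures with the opposite sign. With placebo included, the expected bias is 0 in every row. The percentages are assumptions, not estimates from the protocol.

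**The case against.** The strongest reply is that the protocol makes no claim from this analysis. The Sponsor only may explore it. No hypothesis, test or alpha is attached, and efficacy is judged on the randomized comparison in section 6.6.2, with alpha confined to the primary and secondary endpoints (section 6.3). A parallel placebo display is not forbidden. The dosing halt also followed unfavorable trends in the active arms against placebo, which an optional single-arm display is unlikely to outweigh. All of this stands, and it sets the severity. It does not answer the design point: the active-only restriction is written into the protocol, and following it as written gives an estimate that cannot be interpreted.

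A reader might infer that the 33% fall in step 4 measures the bias and so nearly matches the planned 40% slowing. The documents do not support that. The 33% compares two post-randomization intervals, taken from planning means for a simulation simplified to two timepoints.

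The supporting premises also have limits. The stability criterion covers 12 weeks and does not constrain TFC or cUHDRS slope over the year or more of registry data. The difference in rating between registry and trial is plausible but not documented.

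**Conclusion.** The point holds as a minor one. Section 6.6.6 restricts the within-patient comparison to active patients, so a change in rate unrelated to drug is confounded with a drug effect. The size and direction of the bias are unknown, because the documents give no pre-randomization rate; it could be zero.

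The conclusion rests on two things: the explicit wording of the restriction, and the inference from 1:1:1 allocation that placebo patients with at least 1 year of registry follow-up exist. A reader might go further and infer that the protocol plans to present the result as evidence of efficacy. It does not say so. The primary analysis, its type I error and the sample size are unaffected.

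**What to change.** Reword the last paragraph of section 6.6.6, or settle it in the SAP, as follows.

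- Apply the comparison to all randomized patients in the primary analysis cohort, placebo included, with at least 1 year of ENROLL-HD follow-up before randomization.
- Report the active-minus-placebo difference in change of slope, or in post-randomization slope adjusted for the patient's prior registry slope, labelled exploratory. State the number of contributing patients per arm.
- Use the same data cut-off rule in every arm, for example a common calendar cut-off tied to 22 March 2021. Do not cut each patient at his or her own last on-drug time: that conditions on staying on treatment, and section 6.2 already expects discontinuation to differ by arm (20% placebo, 15% active).
- Show any single-arm before/after change as descriptive only.

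The cost is a few lines of text and the registry link for placebo patients. No new trial assessment is needed. If too few placebo patients have registry history, the analysis can be dropped without loss to the trial's main conclusions.

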6.7 SAFETY ANALYSES

The safety population (see Section [6.1](#)) will be the primary population for all analyses of safety data. Incorrect treatment assignments (patients who received a treatment different than their planned randomized treatment) will be summarized and the impact on the safety assessment will be discussed.

For all safety analyses, patients enrolled prior to implementation of the Version 4 of the protocol will be summarized separately.

All verbatim adverse event terms will be mapped to MedDRA thesaurus terms. The adverse event severity grading scale indicated in [Table 4](#) will be used for assessing adverse event severity. Laboratory values determined as an adverse event should be graded as per [Appendix 6](#), which is based on the NCI CTCAE (v5.0).

All safety data, including adverse events, laboratory tests, CSSR-S, MoCA, ECG, and vital signs will be reported in individual listings and summarized by treatment for each assessment time using descriptive statistics. For continuous variables, both the original value as well as the change from baseline will be reported.

The incidence of adverse events will be summarized on the basis of body systems and dictionary preferred terms. The incidence of adverse events by severity and relationship to study drug or study procedure and incidence of marked abnormal laboratory test results will be provided.

The iDMC will review safety data throughout the study. Analyses required for the iDMC data review will be performed as described in the iDMC Charter.

6.8 PHARMACOKINETIC ANALYSES

For all patients in the PK population (Section 6.1), CSF and plasma concentrations of RO7234292 will be presented descriptively, including arithmetic and geometric means, median, range, standard deviations, and coefficients of variation. Nonlinear mixed-effects modeling will be used to analyze the concentration–time data for RO7234292 in CSF and plasma following IT administration. A covariate analysis will be conducted to evaluate the effect of covariates such as body weight, age, and sex on RO7234292 exposure.

Population and individual estimates of primary PK parameters (e.g., clearance, distribution volume) and secondary PK parameters (e.g., area under the plasma concentration–time curve, average trough plasma concentration) will be computed and used to explore exposure-response relationship on primary and key secondary endpoints, as well as safety measures. The data from this study may be pooled with data from other studies conducted with RO7234292 to support the population PK/PD modeling.

Details of this mixed-effects modeling and exploration of exposure-response analysis and results will be described and reported in a document separate from the Clinical Study Report.

6.9 IMMUNOGENICITY ANALYSES

The immunogenicity analysis population will consist of all patients with at least one ADA assessment. Patients will be grouped according to treatment received or, if no treatment is received prior to study discontinuation, according to treatment assigned.

The numbers and proportions of ADA-positive patients and ADA-negative patients at baseline (baseline prevalence) will be summarized by treatment group. For those who are ADA-positive, titers will be estimated as well as antibody subtype. In addition, the numbers and proportions of ADA-positive patients and ADA-negative patients at baseline (baseline prevalence) and after drug administration (post-baseline incidence) will be summarized for patients on active treatment only. When determining post-baseline incidence, patients are considered to be ADA positive if they are ADA negative or have missing data at baseline but develop an ADA response following study drug exposure (treatment-induced ADA response), or if they are ADA positive at baseline and the titer of one or more post-baseline samples is at least is at least 4-fold greater than the titer of the baseline sample (treatment-enhanced ADA response). Patients are considered to be ADA negative if they are ADA negative or have missing data at baseline and all post-baseline samples are negative, or if they are ADA positive at baseline but do not have any post-baseline samples with a titer that is at least 4-fold greater than the titer of the baseline sample (treatment unaffected).

The relationship between ADA status and safety, efficacy, PK, and biomarker endpoints will be analyzed and reported via descriptive statistics.

6.10 BIOMARKER ANALYSES

The biomarker endpoints are described in Section [2.5](#).

A mixed-effects model repeat measurement model will be used to model the change in each primary and secondary biomarker endpoint, adjusting for the baseline endpoint, CAG repeat length, CAP score, treatment, visit, and treatment-by-visit interaction (the final list of covariates and details of the model will be specified in the SAP).

